1.4 Funding and resources

This is an unfunded study.

2. INTRODUCTION AND BACKGROUND

2.1 Background Information

Across Australia significant injuries result from everyday activities of adults and children. Head injuries are one of the most common injuries that result from activities such as team sports, motor vehicle accidents or falls. The Australian Institute of Health and Welfare reports that the rate of hospitalised injury cases in Australia increased over the last 10 years (2007–08 to 2016–17) by an average of 1% per year. The two main causes of hospitalised injury in 2016–17 were falls (41%) and transport crashes (12%)¹. One of the key concerns for head injury patients is ongoing symptoms of concussion.

It is estimated the annual incidence of concussion is approximately 60-250 per 100,000 of population and of these 17% are sport related (Concussion in Sport Position Statement, 2019)². This is now thought to be of greater significance particularly for school age children and that they should refrain from resuming any physical activity/sport until they are completely symptom-free³.

Head injuries are a common presentation to emergency departments (EDs) for adults and children and symptoms of concussion can be persistent. Early and accurate diagnosis of a traumatic brain injury as well as appropriate management is critical in facilitating good outcomes^{2,4,5}. To date little is known of how concussion is managed in the community by both adults and parents whose child has experienced a head injury and is symptomatic of concussion. Therefore, this study seeks to better

understand the characteristics of people that present with head injuries and symptoms of concussion to an ED and how on discharge concussion is managed in the community.

2.2 Research Question

Phase 1: Primary question: What are the characteristics, patterns and outcomes of people (up to 30 years of age) that present with signs and symptoms of head injuries to one major tertiary referral hospital ED and does the COVID-19 pandemic and social isolation impact on or change the presentation rate for patients with head injuries?

Phase 2: To follow up on a patient's health trajectory journey at 10-14 days and then four weeks post discharge. Follow up will involve exploring the discharge processes, patient symptoms/progress, community management and follow up with a community practitioner.

2.3 Rationale for Current Study

We have very little understanding of the nature, rate, characteristics and outcomes of and for patients who present to a major tertiary referral hospital ED after sustaining a head injury. Head injuries, including concussion, are a serious condition with potential long term health consequences. Currently there is an increased awareness of potential long term outcomes of repeated concussions and the possible association with chronic traumatic encephalopathy⁴. Therefore, early identification and diagnosis of head injuries and such conditions as concussion is important to ensure appropriate care, management and discharge education needs to optimise referral, appropriate community management and follow up care. So that evidence based timely care is provided to patients who present to the ED with a head injury, examination of management and discharge processes need to be explored to optimise patient safety.

It is unclear what constitutes standardised or routine head injury management whilst in the ED. Further, ED head injury discharge processes, management and communication to patients, families and carers remains poorly elucidated. Importantly, the discharge plan and appropriate follow up for this patient cohort remains inconsistent and ad hoc.

Inconsistent management of head injury both within the hospital environment and transition to home in the community may not optimise best patient outcomes. Further, how clinicians communicate the discharge plan and manage activities such as return to work/study and or resuming sporting activities needs to be explored further. In addition, patient compliance and adherence with discharge instructions is also critical for optimising the recovery trajectory, health outcomes and avoidable representations and yet little is known about patient compliance and adherence for this group.

3. STUDY OBJECTIVES

3.1 Primary Objective

Phase 1 To explore the characteristics, patterns and outcomes of patients (up to 30 years of age) that present with signs and symptoms of head injuries to one major tertiary referral hospital ED over a 36 months. To establish the number of patients (up to 30 years of age) who are discharged from ED or admitted to the ward with the diagnosis of head injury.

Phase 2 To follow up on the patient's journey at 10-14 days and four weeks from discharge.

Secondary Objectives

- 1) To determine current ED management and discharge processes for patients with a head injury and discharged home or admitted to the ward.
- 2) How are head injury patients managed in the community and the need for further management.

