Characteristics, patterns and outcomes of patients who present with head injuries to one tertiary emergency department: multi-method study

CONFIDENTIAL

This document is confidential and the property of Royal North Shore Hospital Northern Sydney Local Health District

No part of it may be transmitted, reproduced, published, or used without prior written authorisation from the Institution.

STATEMENT OF COMPLIANCE

This document is a protocol for a clinical research study. The study will be conducted in compliance with all stipulations of this protocol, the conditions of ethics committee approval, the NHMRC National Statement on Ethical Conduct in Human Research (2007) and the Note for Guidance on Good Clinical Practice (CPMP/ICH-135/95)

PROTOCOL SYNOPSIS

Title	Characteristics, patterns and outcomes of head injuries presenting to one tertiary emergency department (ED).
Objectives	
Primary: the incidence of patient presentations to Royal North Shore Hospital (RNSH) ED with head injury.
 
Secondary: to follow up on patient journey at 10-14 days and four weeks from discharge. To review; the discharge process from ED, patient symptoms/progress, community management and the need for further management.

Study Design	Observational Cohort Study
Planned Sample Size	
Phase 1 medical record audit: 36 months (2019/2020/2021) of electronic medical record (eMR) data ~267,000 patients.
 
Phase 2 telephone interview: anticipate recruitment rate of 150 patients.

Selection Criteria	
Phase1: what is the incidence of head injuries and does the pandemic and social isolation impact or change the rate of presentations to ED?
 
Phase 2: patients up to 30 years of age who present to the ED with a head injury then discharged home or admitted to the ward.

Study Procedures	
Identify suitable patients on presentation to ED, review eMR diagnosis/documentation, fill excel data spreadsheet, two follow up phone call interviews (at 10-14 days and four weeks from day of discharge). Qualitative study, data collection including a retrospective record review.
 
Phase 1: retrospective 36 month eMR audit to examine the incidence, characteristics and patterns of patients that present with a head injury before and during the Covid-19 pandemic.
 
Phase 2: telephone follow up of patients (up to 30 years of age) that present to the ED with a head injury and discharged home or admitted to the ward.

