Statistical Procedures	
Sample Size Calculation: phase 1 presentations for 2019 was approx. 89,000 and head injury accounts for 5%; phase 2 estimated at 350 patients. Based on an 80% response participation rate the sample size is estimated to be 280 (up to 30 years of age) participants.
 
Analysis Plan: review data gained from pre-completed excel spreadsheet and information gained from phone call interviews

Duration of the study	
November 2020 – December 2023
 
Retrospectively eMR audit: 1st January 2019 – 31st December 2021

1. Study Management

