4.3 Number of Participants

Phase 1: N=267,000. All patients (up to 30 years of age) presenting to the RNSH ED will be reviewed for evidence of signs and or symptoms of head injuries over a 36 month period to compare pre and during the COVID-19 pandemic. The annual presentation is approx. 89,000 it is anticipated that 5% may have experienced head injury and/or displaying signs/symptoms of head injury. So the anticipated sample size would be approx. 4,450 patients.

Phase 2: N=280. All patients presenting to the RNSH ED and discharged home or admitted to the ward will be invited to participate in a telephone interview. Stratified prospective sample of patients (up to 30 years of age) who present to ED are diagnosed with head injury and discharged home or admitted to the ward. Recruitment will begin from the in 1st January 2021 – 31st December 2021.

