8. STATISTICAL METHODS

The retrospective eMR audit does not require a power calculation as we are not testing an intervention but seeking to explore and characterise service data. Phase 1 data to be collected includes: patient demographic information (age, gender, etc.) and clinical information (for example date/time of arrival, triage category, reason for ED presentation, assessment and diagnostic code, discharge summary, nursing documentation, community referrals, length of stay, disposition, ED clinical space) to determine patients that have presented or discharged with signs/symptoms of head injury or concussion pre COVID 19 and during the pandemic.

For the descriptive exploratory study quantitative data will be presented using descriptive statistics and summarised using frequencies and percentages. Examining for central tendency means, standard deviation (normally distributed data), or median and interquartile range (non-normally distributed data) will be analysed. For continuous data comparison will be conducted using T test and Chi square will be used for categorical data. If the data allows (there are sufficient observations and the distribution of data is appropriate) we will conduct multivariate analyses to explore the determinants of patient compliance with ED discharge information. Quantitative data analysis will be performed using SPSS v.21 and Excel for data cleaning, mining and summaries of data sets. All data will be de-identified.

For Phase 2 involves qualitative interview data obtained from semi-structured telephone interviews. Data to be collected includes: patient demographic information (age, gender, etc.), history including mechanism of injury, signs/ symptoms of concussion, management in ED and follow up plan. All responses provided by patients or their persons responsible will be analysed and organised thematically and stored and managed using NVivo™ v12. Thematic analysis will be guided by Gibbs's (2007) framework which includes: 1) transcription and familiarisation; 2) code building; 3) dis/confirmatory theme development; and 4) data consolidation and interpretation. This framework provides a systematic approach for interpretation (Lichtman, 2010, Brodie and Irving, 2007). The investigators will discuss and review emerging coding and themes.

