8.1 Sample Size Estimation

This is an observational study not requiring a powered sample.

Phase 1 medical record audit: 36 months of ED data characterising approximately 267,000 patients. All data is routinely collected and will be obtained through eMR

Phase 2 telephone interview: anticipate recruitment rate 280 patients or until data saturation is reached.

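### Phase 1 gives its size as patients when the figures are presentations, and the objectives switch between the two units without saying how repeat visits are handled

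*Protocol*

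**What the plan says.** The source figure is a count of visits. The synopsis (Statistical Procedures) says "phase 1 presentations for 2019 was approx. 89,000", and section 4.3 says "The annual presentation is approx. 89,000 it is anticipated that 5% may have experienced head injury".

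The figures built on it are labelled as people. Section 8.1 speaks of "36 months of ED data characterising approximately 267,000 patients", the synopsis does the same under planned sample size, and section 4.3 concludes "So the anticipated sample size would be approx. 4,450 patients".

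The objectives use both units:
- Synopsis, primary objective: "the incidence of patient presentations to Royal North Shore Hospital (RNSH) ED with head injury".
- Section 2.2, pandemic question: a change in the rate of presentation.
- Section 3.1, primary objective: "To establish the number of patients (up to 30 years of age) who are discharged from ED or admitted to the ward".

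On repeat visits, section 9.2 says Phase 1 patients stay identifiable for a short time after the first extraction, so that re-presentation can be measured, and are then coded. Section 6, waiver item (d), says instead that identity is removed when the data are collected. Section 9 says the audit holds de-identified records only.

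On comparisons, section 8 says "For continuous data comparison will be conducted using T test and Chi square will be used for categorical data". Section 1.3 adds ANOVA, Mann-Whitney, Kruskal-Wallis and Fisher's exact test.

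**The concern.** A number of presentations and a number of patients are different quantities as soon as anyone attends twice. The protocol expects that. It plans to measure re-presentation, its rationale (section 2.3) raises repeated concussion and avoidable return visits, and the audit covers 36 months in an age group chosen partly for its exposure to contact sport.

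Two things are at stake. First, if visits are reported as patients, the section 3.1 count is too high, and percentages by age, sex or disposition give extra weight to people who come back. Second, each named test assumes independent observations. Rows from the same person do not meet that assumption, so the pre-pandemic versus pandemic comparison would not have its nominal error rate.

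The de-identification conflict makes the timing matter. If identity is removed at collection, as section 6 says, visits cannot be linked to people afterwards, and no later analysis plan could recover a person count or a clustered analysis.

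**Working it through.** **1. Reproduce the plan's figures.**
- 89,000 presentations a year (synopsis; section 4.3) × 3 years = 267,000. This matches the synopsis and section 8.1.
- 89,000 × 5% = 4,450. This matches section 4.3.

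Both reproduce exactly from visit counts, with no step that converts visits to people. The 4,450 is also a one-year figure; on the same 5%, 36 months gives 267,000 × 5% = 13,350. That mismatch is a separate matter, but 13,350 is the relevant base for the full audit.

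**2. Effect on the count.** The protocol gives no repeat share, so let r be the assumed share of head-injury presentations that are repeat visits. Then

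people = presentations × (1 − r), and overstatement = r / (1 − r).

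| Assumed r | Overstatement | People behind 13,350 presentations |
|---|---|---|
| 3% | 3.1% | 12,950 |
| 5% | 5.3% | 12,683 |
| 10% | 11.1% | 12,015 |
| 15% | 17.6% | 11,348 |

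**3. Effect on a two-period comparison analysed by visit.** Assume each repeat is one person's second visit, with within-person correlation ρ. Let the periods hold n1 and n2 visits, and let k = r(n1 + n2) people have two visits.
- Both visits in the same period, with the same r in each period: the variance of the difference is multiplied by 1 + 2rρ.
- One visit in each period: the variance is σ²(1/n1 + 1/n2) − 2kρσ²/(n1·n2). That is the naive variance multiplied by 1 − 2rρ, whatever the split between periods.

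The true standard error is the naive one times the square root of the multiplier. The actual level of a nominal two-sided 5% test is 2 × [1 − Φ(1.96 / √multiplier)].

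| r, ρ | All repeats in the same period: SE factor, actual level | All repeats across periods: SE factor, actual level |
|---|---|---|
| 3%, 0.3 | 1.01, 5.2% | 0.99, 4.8% |
| 5%, 0.5 | 1.02, 5.6% | 0.97, 4.4% |
| 10%, 0.5 | 1.05, 6.2% | 0.95, 3.9% |
| 15%, 1.0 | 1.14, 8.6% | 0.84, 1.9% |

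Real data would mix the two columns and fall between them. The last row is a ceiling: ρ = 1 suits a fixed trait such as sex, but not visit-level outcomes such as length of stay or triage category.

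**The case against.** The strongest reply is that nothing in the protocol says each visit will be counted as a person. The temporary identification in section 9.2 would let distinct people be counted before coding. The 267,000 is in effect a workload figure (section 6, waiver item (b), uses it for records to be reviewed), no power calculation rests on it, and the reported count will come from the audit itself. The tests are named without defining a row; with one row per person they would not be undermined by repeat visits. The analysis is mainly descriptive, and a clustering adjustment is a detail that a statistical analysis plan, not shown here, may supply.

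Most of this stands, and it limits the point. A reader might infer that the patient count will be biased upward, or that standard errors for the pandemic comparison will be too small. The documents support neither. Overstatement follows only if the labelling in sections 4.3 and 8.1 carries through. The protocol specifies no standard errors or confidence intervals, and repeats that span both periods make the naive error too large.

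The reply does not remove the unit conflict, which lies in the protocol's own objectives and sample figures. Nor does it settle whether linkage will be possible, because section 9.2 disagrees with sections 6 and 9. An analysis plan written after extraction could not repair that.

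**Conclusion.** The point holds as an error of unit and an internal contradiction. The 267,000 and the 4,450 are presentations labelled as patients, the objectives alternate between the two, and the protocol foresees repeat visits without saying how they enter the counts or comparisons.

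The size of the consequence cannot be derived from the documents. Under the assumed repeat share of 3% to 15%, and only if visits are reported as patients, the count would be 3% to 18% too high. The effect on test error is secondary. At 5% repeats and a correlation of 0.5, a nominal 5% test runs between 4.4% and 5.6%, depending on where the repeat visits fall. It becomes material only if repeats are frequent, strongly correlated and concentrated on one side of that contrast. This should be corrected before extraction, but it does not invalidate the study.

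**What to change.** 1. Relabel 267,000 (synopsis, sections 4.3 and 8.1) and 4,450 (section 4.3) as presentations.
2. State the unit for each objective: the presentation for the presentation rate and the pandemic comparison; the person, taken at the first head-injury presentation in the audit, for patient counts, demographics and disposition.
3. Where repeat presentations enter a comparison, use patient-clustered errors (robust or GEE). These handle repeats within a period and across periods.
4. Reconcile section 9.2 with section 6, waiver item (d), and section 9, so that each person receives a coded study number before identity is removed and that code stays in the analysis file.

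The cost is a few sentences and slightly more analysis. It relies on the linkage that section 9.2 already describes, so item 4 has to be settled first; without it, items 2 and 3 cannot be carried out.

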4. STUDY DESIGN

4.1 Type of Study

Observational Study

4.2 Study Design

This is an observational Cohort Study of people that present to a major tertiary hospital with a head injury. The study comprises of two phases;

Phase 1 medical record audit: To explore the characteristics, patterns and outcomes of people (up to 30 years of age) that present with signs and symptoms of head injuries to one major tertiary referral hospital ED comparing pre and during the COVID-19 pandemic.

Phase 2 telephone interviews: Stratified prospective sample of patients (up to 30 years of age) who present to ED and diagnosed with head injury, given written and verbal discharge education / information / instructions and followed up appropriately in the community using telephone interview.

4.3 Number of Participants

Phase 1: N=267,000. All patients (up to 30 years of age) presenting to the RNSH ED will be reviewed for evidence of signs and or symptoms of head injuries over a 36 month period to compare pre and during the COVID-19 pandemic. The annual presentation is approx. 89,000 it is anticipated that 5% may have experienced head injury and/or displaying signs/symptoms of head injury. So the anticipated sample size would be approx. 4,450 patients.

Phase 2: N=280. All patients presenting to the RNSH ED and discharged home or admitted to the ward will be invited to participate in a telephone interview. Stratified prospective sample of patients (up to 30 years of age) who present to ED are diagnosed with head injury and discharged home or admitted to the ward. Recruitment will begin from the in 1st January 2021 – 31st December 2021.

4.4 Study sites

Royal North Shore Hospital Emergency Department

4.5 Expected Duration of Study

November 2020 – December 2023

6 weeks from the last patient included in the study.

4.6 Primary and Secondary Outcome Measures

Primary outcome:

- To explore the characteristics, patterns and outcomes of patients that present with head injuries to one major tertiary referral hospital ED.
- How are head injury patients managed in the community and the need for further management.

Secondary outcomes:

- To compare data both pre and during the COVID-19 pandemic
- Identification of evidence based concussion assessment and management in the ED
- How were head injury patients managed in the ED
- Identification of the type and appropriateness of discharge information, education and instructions
- What discharge instructions were provided for commencing post head injury activities such as return to school, work and sporting activities
- What were the patterns of community referrals

5. PARTICIPANT ENROLLMENT AND RANDOMISATION

5.1 Recruitment

Patients up to the 30 years of age have been included in the study as this patient cohort are more likely to be involved in team contact sports and less likely to have co-morbidities. Posters will be positioned in all areas of the ED (with the exception of the resuscitation bays).

Phase 1: A 36 month (1st January 2019 - 31st December 2021) eMR audit of all patients (up to 30 years of age) presenting to ED will be reviewed for evidence of head injuries. Limitation of snowmed diagnostic codes will require review of all emergency presentations eMR to determine patients that have presented or been discharged with signs/symptoms of head injury or concussion. Review of eMR will be undertaken by the lead researcher to identify participants meeting inclusion criteria for phase 1. Due to the large number of patient records being accessed data for 2021 will only be accessed in early 2022 and as such, will be retrospective in nature.

Phase 2: A 12 month (1st January – December 31st 2021) prospective study of patients (up to 30 years of age) who present to ED with a head injury will be included in the study. The aim of the telephone interview is to collect data after the patient has been discharged from the ED. To obtain information from the patient such as; feedback on the discharge process, ongoing symptoms, return to sport, school, study or work or the need for further medical review.

For phase 2 potential participants will identified then recruited by clinicians or the emergency research volunteers, who will seek written consent whilst they are in the ED to participant in two telephone interviews.

All patients will have the opportunity to opt out of the study without any impact on care practices. Randomisation will occur 1:1 ratio for patients < 16 years of age and patients > 16 years of age to identify 20 participants per week, who will be contacted 10-14 days post injury and then four weeks post discharge. Telephone interviews will be conducted by either ED research volunteers, the lead researcher or associate researchers from the RNSH ED Office. Prior to the commencement of the telephone interview each patient/parent/carer on contact will be again given the opportunity to opt out and verbal consent will be obtained. Each participant will be invited to select an interview schedule time suitable for them. Potential participants will only be contacted three times and if unable to be contacted will be considered as declining to participate in the study. Potential participants will only be contacted between the hours of 0800am until 0600pm (Monday – Friday).

All emergency clinicians will be briefed about the study via email, posters and short in-services.

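### Phase 2's weekly draw of 20, its 12-month window and its stated size (350 patients giving 280 participants) do not agree, and nothing in the protocol reconciles them

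*Protocol*

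**What the plan says.** Section 5.1 describes Phase 2 as "A 12 month (1st January – December 31st 2021) prospective study", and section 4.3 gives the same dates: "Recruitment will begin from the in 1st January 2021 – 31st December 2021". Section 5.1 also sets the selection rule. Patients are drawn at random, in equal numbers from those under and those over 16, and the purpose of the draw is "to identify 20 participants per week, who will be contacted 10-14 days post injury and then four weeks post discharge". It does not call 20 a maximum and does not limit the number of weeks in which the draw is made.

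The size appears in four places:

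- Synopsis, Statistical Procedures: "phase 2 estimated at 350 patients", which the same row converts to the number expected to take part: "Based on an 80% response participation rate the sample size is estimated to be 280 (up to 30 years of age) participants".
- Synopsis, Planned Sample Size: 150 patients for the telephone interviews.
- Section 4.3: 280.
- Section 8.1: "anticipate recruitment rate 280 patients or until data saturation is reached".

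No section connects any of these sizes to the weekly draw.

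**The concern.** A weekly rate and a calendar window together determine how many patients are selected. Here their product is far from every stated size, so staff who follow section 5.1 as written cannot also finish at the stated number.

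The consequence depends on which number gives way:

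- **The size holds and selection stops when it is reached.** The sample covers only the first part of 2021. Section 5.1 justifies the age limit partly by participation in team contact sports, and the interviews ask about return to sport, school, study and work. Patients presenting in the unsampled months would have no chance of selection, and no later analysis can recover them.
- **The draw and the window hold.** The number of patients approached is about three times the number stated. The call load for a study that section 1.4 calls unfunded grows in proportion.

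Phase 2 also supplies the community-management outcome, which section 4.6 lists as primary.

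**Working it through.** **Inputs**

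- Weekly draw: 20, both age strata together at 1:1 (section 5.1), read as 10 + 10.
- Window: 1 January to 31 December 2021, 365 days, 365/7 = 52.1 weeks, taken as 52 (sections 4.3 and 5.1).
- Stated size: 350 patients, 80% participation, 280 participants (synopsis, Statistical Procedures); 280 again in sections 4.3 and 8.1.
- Other stated size: 150 (synopsis, Planned Sample Size).

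**Step 1. Reproduce the protocol's figure.** 350 × 0.80 = 280. The two sizes in the Statistical Procedures row agree with each other.

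**Step 2. Size implied by the draw and the window.**

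- Selected: 20 × 52 = 1,040 (1,043 with 365/7 weeks).
- Interviewed, if the 80% applies to those selected: 1,040 × 0.80 = 832.
- Ratios: 1,040/350 = 2.97 and 832/280 = 2.97. Against 150: 832/150 = 5.5 if 150 means interviewed, or 1,040/150 = 6.9 if it means selected.
- Scheduled calls at two per selected patient: 2 × 1,040 = 2,080, against 2 × 350 = 700.

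If 20 were meant per stratum, the draw would be 40 × 52 = 2,080 patients and the gap would widen.

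**Step 3. Time implied by the draw and the size**, counted from 1 January 2021.

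| Stop at | Weeks at 20 per week | Ends about |
|---|---|---|
| 350 selected | 350/20 = 17.5 | 3 May 2021 |
| 280 selected | 280/20 = 14.0 | 9 April 2021 |
| 150 interviewed (150/0.80 = 187.5 selected) | 187.5/20 = 9.4 | 7 March 2021 |
| 150 selected | 150/20 = 7.5 | 22 February 2021 |

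Stopping at 350 selected covers 17.5/52 = 34% of the stated year.

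**Step 4. Draw implied by the size and the window.** 350/52 = 6.7 per week. Rounded up to 7: 7 × 52 = 364 selected, and 364 × 0.80 = 291 interviewed.

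**Step 5. Can the quota be filled?** Section 4.3 takes 5% of 89,000 annual presentations, 4,450 head injuries a year. 1,040/4,450 = 23%. The 89,000 is given as the annual presentation count, and the share of head injuries that is aged up to 30, eligible and consenting is not stated. A draw of 20 a week is therefore possible only if that share is at least about 23%.

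**The case against.** The strongest reply is that the Phase 2 sizes are loose by design. The synopsis calls them estimates, section 8.1 says no powered sample is needed and allows stopping at saturation, and section 8 analyses the interviews thematically. This stands as a reason to lower the severity: no test or power claim depends on 280. It does not remove the conflict. Section 4.3 states 280 without qualification, and the saturation clause, read naturally, permits stopping at or before 280. It cannot explain 1,040, and it would shorten the sampled period further.

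The 1,040 and 832 also rest on assumptions. The quota may not be filled every week. The protocol does not say that 350 is the number drawn, nor whether the 80% refers to written consent in the emergency department or to verbal consent at the call. The weekly figure may itself be the mistake, or 20 may have been intended as a ceiling, although the text does not say so. All of this stands, which is why the point is that the numbers disagree, not which one is wrong.

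Two stronger readings are tempting, and the documents support neither:

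- A reader might infer that Phase 2 is planned to run only from January to early May. No section says that recruitment closes when the number is reached, and two sections run it to 31 December.
- A reader might compare 350 with a month of head injuries (4,450/12 = 371) and conclude that 350 cannot describe a year. Sections 4.2 and 4.3 call Phase 2 a stratified sample, which may be much smaller than the annual flow. The 4,450 is also derived from the total presentation count, before the Phase 2 exclusions.

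**Conclusion.** The inconsistency is real. A draw of 20 a week for the stated year selects about 1,040 patients and, if the quota is filled and the 80% applies to those selected, yields about 832 interviews. That is about three times the stated 350 and 280, and further from the synopsis's 150. Keeping the draw and stopping at 350 selected would instead end recruitment about 3 May 2021, with about 34% of the year covered; saturation before 280 could end it earlier. The loss of May to December is conditional on such a stop. Its effect on injury type or return to sport is inferred from the protocol's sport rationale; the document gives no seasonal figure.

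This should be fixed because it governs who can enter the sample and costs little to correct. It does not block the study: the phase is unpowered and largely descriptive and thematic.

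**What to change.** 1. State one Phase 2 size in both synopsis rows, section 4.3 and section 8.1, replacing the present mix of 150, 280 and 350. Say whether it counts patients selected or interviewed, and to which step the 80% applies.
2. In section 5.1, derive the weekly draw from that size. For 350 over 52 weeks this is about 7 a week, split evenly between the two age strata over time (for example 3 and 4 in alternating weeks), giving 364 selected and about 291 interviewed at 80%.
3. State that selection is spread over all 52 weeks, and reword the saturation clause in section 8.1 so that it does not close recruitment before 31 December 2021.
4. If 20 a week for the full year is what the sponsor intends, keep it and restate the size as about 1,040 selected and 832 interviewed, after checking that enough eligible patients present and that the calls can be staffed.

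The cost is a text edit in several places, submitted as an amendment under section 10.2. At 7 a week, about 14 more patients are selected than the stated 350 (364 − 350), with fewer calls per week than section 5.1 now implies.
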